Aim. The aim for studies 1a and 1b is to measure foetal HR to see if foetuses at 35-36 weeks GA can differentiate musical timbres (study 1a) and major from minor chords (study 1b).

Hypotheses.

1. Foetuses will show an initial HR deceleration as part of an orienting response after stimulus onset in the first block of experiment 1a and 1b.
2. The amplitude of the initial HR deceleration will decrease over the blocks of both experiments which will reflect habituation to the presented stimuli.
3. The initial HR decrease after stimulus onset will be followed by a slower HR acceleration.
4. The HR acceleration will decrease over the course of each stimulus.
5. If foetuses can discriminate a clarinet, a trumpet, and a violin timbre, a new HR decelerative response will be expected after the first presentation of the second and third timbre in experiment 1a. This response is expected to have an increased amplitude compared to the last block of the previous timbre.
6. If foetuses can discriminate major from minor chords, a new HR decelerative response will be expected after the change to the second chord category in experiment 1b. This response is expected to have an increased amplitude compared to the last block of the previous chord category.
7. Foetal HR responses within the chord categories might differ (C- vs. G- vs. D-major; a- vs. e- vs. d-minor), but this difference would be smaller than the one between the two categories (major vs. minor).

Independent variables. Study 1a: Timbre – clarinet vs. trumpet vs. violin.

Study 1b: Chord – major vs. minor.

Dependent variables. Foetal HR variables, e. g. amplitude, absolute value.

Materials and methods - stimuli. Study 1a will investigate foetal perception and differentiation of a clarinet, a trumpet, and a violin timbre. These timbres were selected not only because they have been used in previous studies (e. g. O'Connell, 2003), but also because they represent three of the primary instrument categories, namely woodwind, brass, and (bowed) string instruments which have distinctive, category-specific temporal and spectral characteristics (e. g. Donnelly & Sheppard, 2014). All audio files have the same note (C4; pitch = 261.63 Hz), a total length of 3.492 seconds and are played at the same volume. The SPL is within the range of the ones used in previous studies and is safe for the foetal auditory system (e. g. Kisilevsky et al., 2004; Lecanuet et al., 2000; Shahidullah & Hepper, 1994). Additionally,

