Procedure. After written informed consent and foetal check-ups, the experimental procedure of the two studies will be explained to the participant. Two exemplary trials of each of the two experiments will then be presented. These are a C4 played by a piano for study 1a and one trial each with a F-major and a f-minor chord for study 1b. Both are also played by a piano. After the participant confirms that she has no further questions and agrees to move on to the actual experiments foetal position and behavioural state will then be identified. Baseline 1 will follow and experiment 1a will start thereafter. Each timbre will be presented in three separate blocks of 30 seconds which are separated by 30 seconds of silence to allow the foetal HR to return to (near) baseline levels in between sound blocks (e. g. Morokuma et al., 2008). The sound blocks include six sounds of 3.492 seconds alternated with 1.508 seconds of silence. This design was chosen based on previous studies which showed successful HR responses to auditory stimuli using blocks of sounds with silence and blocks of no sound in between them (Kisilevksy et al., 1989; Lecanuet et al., 2000; Lee, 2010). The timbre experiment will take 9 minutes. Afterwards, a brief break will follow. Next, baseline 2 will start and the chord stimuli will then be presented in three separate blocks for each chord category. Each of the blocks is also 30 seconds, but the sounds are only 1.327 seconds long and separated by 1.673 seconds

of silence which results in 10 sound presentations per block. The shorter sound length is due to the specific temporal characteristic of the instrument used to play these stimuli as tones played by the piano have a very quick attack and a very short release phase (Müller, 2015). The chord experiment is 6 minutes long.

The order of the stimuli in both experiments as well as the order of the experiments themselves will be counterbalanced across participants to control for possible order effects.

Data analyses. Foetal HR will be analysed in two separate two-way repeated analyses of variances (ANOVA) to compare foetal responses to the three different timbres (study 1a) as well as between major and minor chords (study 1b).

Degrees of freedom will be adjusted if the assumption of sphericity is violated in either of the analyses. Post hoc comparisons will be done with Tukey tests ($p < .05$) and Bonferroni-correction will be used for α -adjustment to take multiple comparisons into account.

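### The planned heart-rate ANOVA compares stimulus identities and does not test the recovery at a stimulus change by which hypotheses 5 and 6 define discrimination

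*Protocol*

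**What the plan says.** All references are to the protocol.

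- **Hypotheses (section 6).** Hypothesis 5 states that, if foetuses can tell the timbres apart, "a new HR decelerative response will be expected after the first presentation of the second and third timbre in experiment 1a". It also fixes the comparator: "This response is expected to have an increased amplitude compared to the last block of the previous timbre". Hypothesis 6 does the same for chords: "a new HR decelerative response will be expected after the change to the second chord category in experiment 1b", again against the last block of the preceding category.
- **Independent and dependent variables (section 6).** The factor is stimulus identity: "Study 1a: Timbre – clarinet vs. trumpet vs. violin", and major versus minor in 1b. The outcome is given as "Foetal HR variables, e. g. amplitude, absolute value".
- **Procedure (section 6).** Each timbre and each chord category is played in three 30-second blocks. The order of stimuli "will be counterbalanced across participants to control for possible order effects".
- **Data analyses (section 6).** The plan is for "two-way repeated analyses of variances (ANOVA) to compare foetal responses to the three different timbres" in 1a, and major with minor in 1b. The second factor is not named. Tukey and Bonferroni post hoc comparisons are planned, without saying which cells are compared.
- **Sample size (section 14).** f = .1, α = .05, power .95 and correlation .50 give N = 84 for the heart-rate timbre experiment (18 trials per condition) and N = 60 for the heart-rate chord experiment (30 trials per category).

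**The concern.** The hypotheses ask whether the response comes back when the stimulus changes. The analysis asks whether the average response differs between clarinet, trumpet and violin, or between major and minor. Counterbalancing makes stimulus identity independent of serial position, so the second question carries no information about the first unless the stimuli themselves evoke responses of different size.

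Two misreadings are possible. Foetuses that discriminate as hypothesis 5 describes could give a non-significant timbre effect, reported as no discrimination. Or a significant timbre or block effect could be reported as support for hypotheses 5 and 6 although no recovery at the change was tested. Timbre discrimination, research question 2, is the purpose of study 1a.

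**Working it through.** **1. What the two-way ANOVA can contain.** The second factor is unnamed. Serial position cannot be fully crossed with timbre within a foetus: each foetus hears each timbre in one position only, so 3 of the 9 timbre-by-position cells are filled. Block (1 to 3) is the natural remaining factor, and I assume it below.

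**2. Expected values under two patterns (assumed; in SD of deceleration amplitude).**

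- *Full discrimination, equal responses:* 1.0, 0.7, 0.5 in blocks 1 to 3 of every timbre.
  - Mean for each timbre, whatever its position: (1.0 + 0.7 + 0.5)/3 = 0.73. The timbres do not differ, and neither do their block profiles.
  - Change contrast: 1.0 − 0.5 = 0.5 at each change.
- *No discrimination, one continuous decay over nine blocks:* 1.0, 0.7, 0.5 | 0.4, 0.35, 0.3 | 0.3, 0.3, 0.3.
  - Block 1 mean over positions: (1.0 + 0.4 + 0.3)/3 = 0.57. Block 3 mean: (0.5 + 0.3 + 0.3)/3 = 0.37. The difference is +0.20 although nothing recovers.
  - Change contrasts: 0.4 − 0.5 = −0.1 and 0.3 − 0.3 = 0, mean −0.05.

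**3. Simulation.** N = 84, within-foetus correlation .5, six orders in equal numbers, 3000 runs, tests at 5 %. The change contrast is the mean of the two changes, tested one-sided in the hypothesised direction.

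| Test | Full discrimination | No discrimination |
|---|---|---|
| Timbre | 4.3 % | 1.5 % |
| Timbre × block | 5.0 % | 4.1 % |
| Block | 100 % | 82 % |
| Change contrast | 100 % | 1.3 % |

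Other assumed shapes agree. With blocks at 1, 0.6, 0.3 of a first-block amplitude of 0.5 to 2 SD, and decay by a factor 0.6 per block without discrimination:

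- *Timbres, N = 84, discriminating:* timbre 4.6–5.0 %, interaction 4.9–5.7 %, change contrast 99.8–100 %. Not discriminating: block 47–100 %.
- *Chords, N = 60, discriminating:* category 4.4–5.0 %, interaction 4.7–5.4 %, change contrast 85–100 %.

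**4. Dependence on equal responses.** Scaling the discriminating pattern by timbre raises the timbre rejection rate to about 54 % at 1.1 : 1 : 0.9, 88 % at 1.15 : 1 : 0.85 and 99 % at 1.2 : 1 : 0.8.

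**5. What the stated N powers.** For a within-subject effect, λ = f²·N·m/(1 − ρ), df1 = m − 1, df2 = (N − g)(m − 1).

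- *Study 1a, m = 18 trials, g = 3:* at N = 84, λ = 0.01 × 84 × 18/0.5 = 30.24, df 17 and 1377, power .957. The next smaller multiple of 3, N = 81, gives .948. The stated 84 is reproduced.
- *Heart-rate chords, m = 30, g = 2:* N = 60 gives .953 and N = 58 gives .945. The stated 60 is reproduced.

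These settings describe an effect across 18 or 30 repeated trials, not the change contrast. For one paired contrast (m = 2), λ = 0.01 × N × 2/0.5 = 0.04·N, so dz = √0.04 = 0.2. Two-sided results:

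| | N = 84 | N = 60 |
|---|---|---|
| Power at dz = 0.2, α = .05 | 44 % | 33 % |
| Power at dz = 0.2, α = .025 (first step of a two-test Holm adjustment) | 33 % | not needed: one change |
| dz detectable with 95 % power, α = .05 | 0.40 | 0.47 |

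At dz = 0.2, 95 % power needs N = 327. The assumed 0.5 SD recovery is much larger: one block difference has variance 2(1 − .5) = 1, so dz = 0.5 and power is 99.5 % at N = 84.

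**The case against.** **The identity comparison serves stated aims.** This stands. Research question 3 asks whether heart-rate responses to major and minor chords differ, and hypothesis 7 compares response sizes between the categories. The ANOVA suits both and should stay. A reader might infer that research questions 2 and 3 cannot be answered at all; the documents do not support that.

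**The null needs equal responses.** This also stands. A reader might infer that perfect discrimination must give a null ANOVA. It need not: modestly unequal responses make the timbre effect significant (step 4), and section 6 chose the timbres for their distinctive acoustic character. On the other side, the sounds share note, length and volume, the chords are matched for amplitude, and no hypothesis predicts that one timbre evokes the larger response. A timbre effect between matched sounds is evidence of differing responses, but not of the recovery that hypothesis 5 requires.

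**Post hoc tests, or an SAP not shown, could supply the contrast.** This is why it is wrong to say that the plan cannot detect discrimination. But cell comparisons from a timbre-by-block ANOVA pool over orders. One given timbre directly precedes another in only 2 of 6 orders, and a block 1 minus block 3 difference is +0.20 SD without any recovery (step 2). The point is not missing detail: the comparison that is stated differs from the one the hypotheses define.

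**Averaging could cancel deceleration against the later acceleration.** A reader might infer this from the loosely worded outcome. The protocol nowhere says that heart rate is averaged over a block, and hypotheses 2, 5 and 6 are framed in amplitude, so this is not part of the point.

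**Conclusion.** The stated timbre and chord-category comparisons do not test hypotheses 5 and 6. This follows from the text alone: a contrast at the change is hypothesised, and a contrast of identities is analysed.

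The size depends on assumptions that the protocol does not give: block as second factor, similar orienting responses to each stimulus, a recovery of 0.5 SD and correlation .5. Under these, at N = 84, the stimulus effect and its interaction reject in about 5 % of trials against about 100 % for the change contrast. The block effect does not fill the gap, rejecting in about 82 % of trials without discrimination under the assumed decay. If responses differ by stimulus, the ANOVA may be significant, but it then answers a different question. The wording should be corrected before any data are analysed.

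**What to change.** In section 6, Data analyses, name the main test for hypotheses 5 and 6: on deceleration amplitude, indexed by serial position, the first block after each change minus the last block before it. Study 1a has two such changes, to be adjusted for multiplicity (Holm, for example); study 1b has one. State that the timbre and major/minor ANOVA is kept for research question 3 and hypothesis 7, and that its block effect bears on habituation (hypothesis 2). A mixed model for the contrast is optional.

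The cost is protocol or SAP wording and a recoding of the same recordings. The downside must be disclosed: N = 84 and N = 60 were not calculated for this contrast. With f = .1 and correlation .50 a single change has about 44 % power at N = 84 and 33 % at N = 60. Section 14 should therefore restate the detectable effect for each change (95 % power at dz of about 0.40 for 84 and 0.47 for 60, before multiplicity adjustment; about 0.43 for 84 at α = .025), or resize the studies if smaller recoveries matter.

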
Each session will be recorded and saved on two external hard drives as well as stored in a secure folder on the university server for later analyses.

Procedure. The experimental procedure of the two studies will be explained to the participant after giving written informed consent and after foetal check-ups have been performed. Two exemplary trials of each of the two experiments will then be presented. These are a C4 played by a piano for study 2a and one trial each with a F-major and a f-minor chord for study 2b. Both are also played by a piano. After the participant confirms that she has no further questions and agrees to move on to the actual experiments foetal position and behavioural state will be identified. Then, baseline 1 will follow and experiment 2a will start thereafter. The three different timbres will be presented 24 times each in a semi-randomised order. Thus, unlike to

experiment 1a no block-design will be used which is also true for experiment 2b. A semi-randomised presentation of the stimuli was chosen because fNIRS is an event related measure of brain activity. This means that brain activity can be measured every time a change in the environment takes place. Every trial of study 2a includes 3.492 seconds of sound and is 11 seconds long (ratio 1:2.15). The whole experiment will take 13 minutes and 12 seconds. Afterwards, a brief break will follow. Then, baseline 2 will start and the chord stimuli will be presented thereafter. Both major and minor chords will be presented 24 times which means that each individual chord will be played eight times, also in a semi-randomised order. All trials are 4.180 seconds long and include 1.327 seconds of sound plus 2.853 seconds ISI (ratio 1:2.15). Experiment 2b is 3 minutes and 20.640 seconds long.

The order of the stimuli will be counterbalanced across participants in both experiments.

Data analyses. Foetal brain activity will be analysed in two separate one-way repeated ANOVA to compare foetal responses to the three different timbres (study 2a) as well as between major and minor chords (study 2b).

Degrees of freedom will be adjusted if the assumption of sphericity is violated in either of the analyses. Post hoc comparisons will be done with Tukey tests ($p < .05$) and Bonferroni-correction will be used for α -adjustment to take multiple comparisons into account.

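### As written, the post hoc rule corrects the three timbre pairs twice (Tukey, then Bonferroni), which costs about a third to two fifths of pairwise power; the fault is conservative.

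*Protocol*

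**What the plan says.** For the heart-rate studies, Protocol Section 6 (Data analyses) states: "Foetal HR will be analysed in two separate two-way repeated analyses of variances (ANOVA"). Section 7 does the same for the fNIRS studies: "Foetal brain activity will be analysed in two separate one-way repeated ANOVA". The second factor of the two-way analysis is not named.

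Both sections then give one identical follow-up rule: "Post hoc comparisons will be done with Tukey tests ($p < .05$) and Bonferroni-correction will be used". The same sentence gives the purpose of the second step: "Bonferroni-correction will be used for α -adjustment to take multiple comparisons into account". No number of comparisons is given, and no family other than the post hoc comparisons is mentioned. Just before this, both sections state: "Degrees of freedom will be adjusted if the assumption of sphericity is violated in either of the analyses". Nothing similar is said for the post hoc tests.

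The factors are "Study 1a: Timbre – clarinet vs. trumpet vs. violin" (three levels, three pairs) and "Study 1b: Chord – major vs. minor" (two levels, one pair). Studies 2a and 2b use the same factors. Section 13 (Statistical plan) adds no method. Section 14 sizes the studies on f = .1, α = .05, power .95 and a correlation of .50.

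**The concern.** Tukey's test is itself a multiplicity correction: its critical value comes from the studentized range, so the chance of any false pairwise difference is held at α. The only purpose the protocol gives for Bonferroni is the one Tukey already serves. Dividing α again by the number of pairs pushes the error rate well under the level the protocol intends, and power is lost in return.

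The timbre pairs are where studies 1a and 2a would show which instruments are told apart. Section 14 says a small effect was chosen to give the best chance of detecting something, and a second correction works against that aim. A null post hoc result could then be read as absence of discrimination when it partly reflects the doubled threshold.

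**Working it through.** **Inputs (Section 14).** f = .1, α = .05, power .95, ρ = .50. N = 84 for study 1a (18 trials per condition), 60 for the HR chord experiment (30 trials), 69 for 2a and 70 for 2b (24 trials each).

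**1. The plan's own figures.** I used the repeated-measures within-factor F test, with λ = f²·N·m/(1−ρ), df1 = m−1 and df2 = (N−G)(m−1). Here m is trials per condition and G the number of stimulus categories.

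| Study | G | m | N | λ | df1, df2 | Power |
|---|---|---|---|---|---|---|
| 1a | 3 | 18 | 84 | .01·84·18/.5 = 30.24 | 17, 1377 | .957 |
| HR chord | 2 | 30 | 60 | 36.0 | 29, 1682 | .953 |
| 2a | 3 | 24 | 69 | 33.12 | 23, 1518 | .953 |
| 2b | 2 | 24 | 70 | 33.6 | 23, 1564 | .957 |

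All four stated N reproduce. They concern the omnibus F test at an unadjusted α of .05, so the post hoc rule does not touch them.

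**2. From f = .1 to a pairwise difference.** With three means, f is the SD of the means divided by σ.
- One timbre differs from two equal ones: d·√2/3 = .1, so d = .3/√2 = .212.
- Means evenly spaced: the extreme pair differs by d = .1·√6 = .245. The adjacent pairs differ by half that.

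With ρ = .50 the SD of a paired difference is σ·√(2(1−.5)) = σ, so the noncentrality is d·√N. For N = 84 this is .212·9.165 = 1.94 and .245·9.165 = 2.24. For N = 69 it is 1.76 and 2.03.

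**3. Critical values.** Three levels, pooled repeated-measures error, df = 2(N−1), critical t = q/√2.
- N = 84 (df 166), Tukey at .05: q = 3.345, t = 2.365, per-pair p = .0192.
- N = 84, Tukey at .05/3 = .0167: q = 3.930, t = 2.779, per-pair p = .0061.
- N = 69 (df 136): t = 2.370 and 2.786.

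The nominal family-wise level under the doubled rule is .0167.

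**4. Pairwise power (noncentral t).**

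| Study | d | Tukey alone | Tukey at .05/3 | Points lost | Share lost |
|---|---|---|---|---|---|
| 1a, N = 84 | .212 | .340 | .206 | 13 | 39% |
| 1a, N = 84 | .245 | .454 | .300 | 15 | 34% |
| 2a, N = 69 | .212 | .275 | .157 | 12 | 43% |
| 2a, N = 69 | .245 | .372 | .231 | 14 | 38% |

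To regain the Tukey power of .454 at d = .245 under the doubled rule, study 1a would need about 118 participants instead of 84. With a divisor of 2 instead of 3, power at N = 84 would be .25 to .35.

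**5. Chord main effect.** Two levels give one pair. Tukey then equals the t-test (critical t 2.001 at N = 60 either way) and the divisor is 1, so nothing changes.

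**6. Cell-level comparisons, on assumptions the protocol does not state.** Suppose block is the second factor in study 1a and all pairs of the 3 × 3 = 9 cells are tested. There are then 9·8/2 = 36 pairs, with df = 83·8 = 664. Critical t rises from 3.112 to 4.123, and the nominal family-wise level is .05/36 = .0014. At an assumed d = .4 (noncentrality .4·9.165 = 3.67), power falls from .71 to .33.

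**The case against.** The strongest reply is that Bonferroni may be meant for something Tukey does not cover. Section 6 lists several heart-rate variables as outcomes, Section 7 lists HbO₂ and HbR, and each set of studies has two ANOVAs. A Bonferroni division across any of these would be legitimate and would not be a double correction. This stands as a possibility. But the sentence ties Bonferroni to the post hoc comparisons and names no other family or divisor, so it needs changing on either reading. It also means that simply deleting Bonferroni would be unwise, since it may be the only control intended across outcomes.

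Three stronger inferences are tempting and are not supported.

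- **That family-wise error collapses to about .001.** This holds only in the 36-pair case. The protocol names neither the second factor nor that family, and d = .4 is not its effect size. Hypotheses 5 and 6 do compare particular blocks, so cell-level contrasts are relevant, but they do not call for all 36 pairs.
- **That pooled-error Tukey tests inflate false positives when sphericity fails.** In an illustrative simulation (N = 84, one condition with twice the residual SD), Tukey alone gave a per-pair error of up to .038 against the intended .019, and a family-wise error of .060. Under the doubled rule the same example gave .015 and .024, so the plan as written shows no inflation. The protocol also does not say that a pooled term will be used.
- **That the rule is wrong for the chord factor.** For a two-level main effect it is redundant and harmless.

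It is also fair to say that pairwise power at f = .1 is below one half even with Tukey alone. The double correction worsens a weak test; it does not spoil a strong one.

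**Conclusion.** The point holds for the three timbre pairs. The rule as written corrects one family twice, giving a nominal family-wise level of about .017 and a loss of 12 to 15 percentage points of pairwise power (34–43% of it) in studies 1a and 2a. These figures rest on a divisor of 3, the protocol's f = .1 and ρ = .50, a pooled error term with sphericity, and the two mean patterns shown. The larger cell-level loss is conditional on block being the second factor and on all 36 pairs being tested, so it should not be quoted as the plan's operating characteristic.

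The fault is conservative: it risks missed differences and does not create false positives. It leaves untouched the omnibus tests, the stated N, study 2b and the chord main effect in study 1b. It should be corrected, but it does not threaten the design.

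**What to change.** In the Data analyses paragraphs of Sections 6 and 7, replace the sentence with one procedure per family:

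- For the three timbre pairs, use Holm-adjusted paired t-tests, each with its own error term. This also removes any reliance on a pooled error term if sphericity fails.
- Test the change contrasts of hypotheses 5 and 6 as planned contrasts, with Holm across the contrasts in hypothesis 5.
- If Bonferroni is meant for another family (several HR variables, HbO₂ and HbR, or the two experiments), keep it for that family only, name the family and state the divisor.

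The cost is a text edit in two sections, with no change to data collection or recruitment. There is one small price. When sphericity holds, Bonferroni-adjusted paired t-tests (df 83, critical t 2.443) have power .31–.43 at N = 84, against .34–.45 for Tukey alone. Holm is never less powerful than Bonferroni. Either is clearly better than the .21–.30 of the doubled rule.

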Aims. Studies 2a and 2b use fNIRS to investigate foetal brain responses in fronto-temporal areas following the presentation of different musical timbres and chords. One aim is to find out if it is possible to measure foetal brain activity with fNIRS in general. The second aim is to see if fetuses at 35-36 weeks GA can differentiate musical timbres (study 2a) and major from minor chords (study 2b) on a cortical level.

Hypotheses.

1. It is possible to measure foetal brain activity with fNIRS.
2. Differentiating brain responses will be expected if fetuses can discriminate a clarinet, a trumpet, and a violin timbre.

Auditory Perception of the Foetus – Study Protocol

3. If foetuses can discriminate major from minor chords, this will be reflected in differentiating brain activity patterns after the presentation of major and minor chords.
4. Foetal brain activity responses within the chord categories might differ (C- vs. G- vs. D-major; a- vs. e- vs. d-minor), but this difference would be smaller than the one between the two categories (major vs. minor).

Independent variables. Study 2a: Timbre – clarinet vs. trumpet vs. violin.

Study 2b: Chord – major vs. minor.

Dependent variables. Foetal brain activity, e. g. HbO₂ and HbR.

Materials and methods - stimuli. Same as for studies 1a and 1b (see above).

Materials and methods - image acquisition. A qualified and experienced sonographer will use a Philips Epiq7 Elite Ultrasound System with either a 5C1 or 9C2 transducer (thermal index for bones < 0.3) to perform foetal check-ups, determine foetal position, foetal behavioural state, and to estimate the correct placement of the fNIRS probe. The later one will be a custom-made device consisting of one light emitter and one light detector which will be placed directly on the maternal skin. The fNIRS probe will be using two wavelengths, namely 690 nm and 830 nm, which are known to be optimal for measuring deoxy- and oxygenated blood in early developmental populations (for reviews, see Lloyd-Fox et al., 2010; Wilcox & Biondi, 2015). These wavelengths also possess the physical characteristics to enable penetration of human tissue (León-Carrión & León-Domínguez, 2012; Strangman et al., 2002). The strength of the near-infrared light will be adjusted based on the individual thickness of the maternal tissue. This will enable a consistent sensitivity to measure foetal brain activity across participants and ensure that light levels are well within boundaries for safe use.

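### Study 2b: hypothesis 4 compares chord differences within and between categories, but the planned one-way ANOVA contains only major versus minor

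*Protocol*

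**What the plan says.** **Hypotheses.** Section 7, hypothesis 4: "Foetal brain activity responses within the chord categories might differ", naming the three major and the three minor chords. It then adds the comparative part: "but this difference would be smaller than the one between the two categories (major vs. minor"). Section 6, hypothesis 7 makes the same prediction for heart rate: "Foetal HR responses within the chord categories might differ".

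**Independent variables.** Section 7 gives "Study 2b: Chord – major vs. minor" and section 6 gives "Study 1b: Chord – major vs. minor". Individual chord is listed in neither.

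**Models.** Section 7, Data analyses: "Foetal brain activity will be analysed in two separate one-way repeated ANOVA", which for 2b compares major with minor. Section 6, Data analyses, plans two-way repeated-measures ANOVAs for the heart-rate studies. For 1b only major versus minor is identified, and the second factor is not named. Both sections add Tukey and Bonferroni post hoc comparisons without mentioning single chords. The exploratory regressions cover sex and foetal state (plus baseline heart-rate variability in section 6), not chord.

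**Data.** Section 7, Procedure: there are 24 presentations per category in 2b, and "each individual chord will be played eight times". Section 6, Procedure: 1b has three 30-second blocks per category with ten sounds each. How the three chords are assigned to those blocks is not stated.

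**The concern.** Hypothesis 4 is a numbered hypothesis about the relative size of two differences. The analysis named for study 2b estimates one of them, the category difference. The three chords of a category are pooled, so the differences among them are either averaged away or left in the residual.

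This also affects how hypothesis 3, the main chord hypothesis of study 2b, can be read. A significant major-minor difference could come from all three chords of a category or from a single one. The stimuli make this a practical concern. The major chords are built on C, G and D and the minor chords on A, E and D, so only one root occurs in both sets and category is not the only feature that differs.

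**Working it through.** **1. Check the layout of 2b.** Six chords × 8 presentations = 48 trials. 48 × 4.180 s = 200.64 s = 3 min 20.640 s, which is the stated duration. So the planned session does contain eight trials for each chord.

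**2. Check the sample-size section for a chord term.** Section 14 gives N = 70 for 24 trials per chord category, with f = .1, α = .05, power .95 and ρ = .50. This is reproduced by a within-factor noncentral F test with m = 24 trials as levels and k = 2 categories as groups:
- λ = f²·N·m/(1 − ρ) = 0.01 × 70 × 24 / 0.5 = 33.6
- df = 23 and (70 − 2) × 23 = 1564
- power = 0.957

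Individual chord does not enter. Whether that calculation suits the planned test is a separate question.

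**3. Count degrees of freedom.** Six chords: 6 − 1 = 5. Category: 2 − 1 = 1. Chord within category: 2 × (3 − 1) = 4. The one-way, two-level ANOVA has the 1 and omits the 4. Post hoc tests on a two-level factor add nothing to its own F test.

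**4. Show that the omission matters.** Let all minor chords have mean response 0, and compare two patterns for the major chords.

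| Major chords | Category difference | Largest within-category difference | Mean over the six within-category pairs | Hypothesis 4 |
|---|---|---|---|---|
| 1, 1, 1 | 1 | 0 | 0 | true |
| 3, 0, 0 | 3/3 = 1 | 3 | (3 + 3 + 0 + 0 + 0 + 0)/6 = 1 | false |

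The category means are identical, so the planned ANOVA estimates the same effect in both rows. What separates the rows is not in the model.

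**5. Check which replacement test would be safe.** Two shortcuts fail.
- *Comparing significance.* A chord mean rests on 8 trials and a category mean on 24. With independent trial noise and no foetus-by-chord or foetus-by-category variation (assumptions), the standard error of a chord difference is √(24/8) = 1.73 times that of the category difference. A non-significant chord difference beside a significant category difference therefore does not show that the chord difference is smaller.
- *Requiring a variance ratio above 1.* Suppose the chords lie at 0, d/2 and d within each category, and the category difference is also d. Hypothesis 4, read on the largest difference, is then false. The category mean square is 2 × 24 × (d/2)² / 1 = 12d². The chord-within-category mean square is 2 × 8 × (d²/4 + 0 + d²/4) / 4 = 2d². The noise-free ratio is 6, so the rule would support a false hypothesis.

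**6. Study 1b.** The two-way ANOVA has room for a second factor. Block is likely, because hypothesis 2 of section 6 concerns habituation over blocks, but the protocol does not say so. If each block holds one chord, chord and block position coincide within a foetus, and only counterbalancing across foetuses can separate them. If chords are mixed within a block, sounds follow every 1.327 + 1.673 = 3 s, while section 6 cites heart-rate responses peaking at about 5 s or at 10–20 s, so single-chord responses would overlap. Even with chord as the second factor, the usual F tests do not test whether one difference is smaller than another.

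**The case against.** The best defence is that this belongs in a statistical analysis plan. The research questions and aims concern major versus minor only, hypotheses 4 and 7 are worded cautiously, and nothing rules out a later chord-level analysis, which the 2b data permit. Part of this stands: these are subsidiary hypotheses and the exact contrast could be set elsewhere. But for 2b the protocol is not silent. It states the hypothesis, the independent variable and the type of ANOVA, and these do not fit together. A later plan would have to replace the stated model, not just add detail to it.

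Three stronger readings are tempting, and the protocol does not support them.
- *That both chord ANOVAs contain only major versus minor.* This is true of 2b. The 1b model is two-way, so there one can say only that the second factor, the chord layout and a test of hypothesis 7 are not stated.
- *That hypothesis 4 would be falsely confirmed at some calculable rate.* That needs a decision rule based on patterns of significance, an assumed power and a chord pattern. The protocol contains no such rule, so no rate is given here.
- *That the major-minor test is invalid.* It remains a test of the mean difference between these two sets of chords. The limit is on attributing that difference to category.

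**Conclusion.** The point holds firmly for study 2b: the stated factor and model leave out 4 of the 5 degrees of freedom among the six chords, so hypothesis 4 has no test and a single deviant chord cannot be told from a category effect. This follows from the stated text and the count in step 3; it needs no assumption about effect size or power. For study 1b the supportable statement is that hypothesis 7 has no stated test and that the protocol does not show whether chord can be separated from block position.

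The matter should be corrected, but it is moderate in weight. It concerns subsidiary hypotheses and the interpretation of the main chord comparison. The design and the data collection are not at fault.

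**What to change.** **Study 2b.**
- Add chord (three levels, nested in category) to the independent variables and to the same repeated-measures model.
- Report the six chord means with confidence intervals.
- Test hypothesis 4 with one pre-specified contrast on the difference scale. One example is the absolute major-minor difference minus a typical within-category pairwise difference (such as the root mean square over the six pairs, corrected for sampling noise), with an interval bootstrapped over foetuses. The correction is needed because chord means rest on fewer trials than category means. Hypothesis 4 is supported only if the interval lies above zero; if it includes zero, call the result inconclusive.
- Alternatively, label hypothesis 4 descriptive and report the chord means only. This is also the sensible choice if the interval is expected to be wide, since section 14 did not size the study for this contrast.
- Do not infer hypothesis 4 from the category test being significant and the chord tests not, or from an undefined variance ratio exceeding 1.

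**Study 1b.** Name the second ANOVA factor and state how chords are assigned to blocks. Apply the same contrast only if chord can be separated from block position, for example with one chord per block and chord order counterbalanced across foetuses. Otherwise label hypothesis 7 descriptive.

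**Cost.** Analysis wording, plus one sentence on the block layout in 1b. The eight presentations per chord in 2b are already planned, and no participants or session time are added.
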